6. STUDY DRUG ADMINISTRATION AND MANAGEMENT

6.1. Study Medication

6.1.1. Abaloparatide

Abaloparatide injection is supplied as a sterile, colorless, clear solution in a glass cartridge which is pre-assembled into a disposable single- subject-use pen. The pen is intended to deliver 30 once daily abaloparatide doses of 80 µg in 40 µL of solution. Each pen contains 3120 mcg/1.56 mL.

Additional information will be provided to clinical sites in a separate Pharmacy Manual including instructions on how to use the injection pen.

6.2. Packaging, Labeling and Storage

6.2.1. Packaging and Labeling

Abaloparatide will be supplied and packaged as injection pens. All packaging operations will be performed in accordance with Good Manufacturing Practices (GMP).

All Investigational Product (IP) will be supplied to study sites packaged and labeled according to local regulations with a statement that all IP is limited to investigational use only. A detailed study drug dispensation plan will be provided in the Pharmacy Manual.

6.2.2. Storage

While at the clinical site, abaloparatide injection pens must be stored in a secure, limited access, temperature monitored refrigerator at 2°C to 8°C (36°F to 46°F) until dispensed for use to a study subject or until returned to the Sponsor.

After the abaloparatide injection pen is used for the first time, the pen may be stored for 30 days at room temperature, 20°C to 25°C (68°F to 77°F). Unused pens should be refrigerated until use. Instructions regarding the storage and handling of the study drug after dispensation to subjects will be provided to sites in the Pharmacy manual.

6.3. Treatment Assignment

All subjects who sign informed consent for the study will be assigned a unique 6-digit subject number which will be used to identify subjects throughout the study and on the eCRFs. Subject numbers will be assigned as follows:

XXX YYY, where:

- XXX represents the study site number;
- YYY represents the subject ID number

6.4. Dosing and Administration

Subjects will self-administer a single daily dose of 80 µg of study medication (abaloparatide) during the Treatment Period.

The first self-administration is to occur at the study site under observation. On the days of clinic visits, study medication must be administered in the clinic to accommodate procedures. Study personnel may administer the study medication during clinic visits.

Subjects will be trained by study personnel during the Pretreatment Period how to self-inject study medication with the abaloparatide injection pen. If a subject requires assistance with study medication administration, an individual (eg, a family member) who has been trained by study personnel may provide assistance.

Subjects will also be provided written instructions on how to use the abaloparatide injection pen. Subjects will be instructed by the study site to inspect the contents of their injection pen before each injection. If the cartridge contents are not clear and colorless, or if the contents contain particles, the subjects will be instructed not to use the pen and to contact the study site for further guidance. Injections should be administered at the same time each day. If a dose is missed, the dose should be administered as soon as possible up to 12 hours after the missed injection. Any time thereafter, the dose should be skipped and the drug should be administered at the next scheduled time the following day. All injections are to be given in the periumbilical region of the abdomen, rotating the site of injection each day, and administered at approximately the same time every day. If it is deemed medically necessary by the Investigator for an injection to be administered at a site other than the abdomen, the alternate site of injection is to be recorded and the reason for the change documented in the medical chart and eCRF as a protocol deviation. On the first day of study medication administration, the subject should self-inject while in a sitting or lying position at the study site and remain in that position for approximately 5 minutes. The subject is to remain under observation for a minimum of 60 minutes after the initial injection. A blood pressure measurement will be taken 60 minutes after the injection. Subjects are to be instructed to self-inject at home in a location where they have the ability to sit or lie down.

Subjects will be instructed to use a new pen after each 30-day period. At each clinic visit during the Treatment Period, the used abaloparatide injection pens should be returned. Compliance, adverse events, and use of concomitant medications should be reviewed upon drug re-supply and documented accordingly in the drug accountability log and eCRF.

6.5. Treatment Compliance

To ensure treatment compliance, the Investigator or designee will supervise all study drug administration that occurs at the site. At each study visit, the Investigator or designee will review subject compliance with study drug administration and remind the subject of study drug dosing requirements. Subject compliance will be ascertained by two methods: subject diaries and measuring residual drug in the cartridge.

Discrepancies between expected and actual dosing will be assessed and discussed with the subject. All discrepancies, causes and subject retraining will be documented in the medical charts, and recorded in the eCRF as appropriate. If a subject does not take all study medication (abaloparatide) as required, the reason for the missed dose is to be discussed with the subject during the visit.

Although calcium and vitamin D are considered concomitant medications for this study, missed doses of calcium and vitamin D will be determined by performing a pill count. If a subject demonstrates continued noncompliance with required abaloparatide dosing despite educational efforts, the Investigator should contact the Sponsor Medical Monitor to discuss discontinuation of the subject from the Study.

6.6. Study Drug Accountability

The Investigator or designated site staff will maintain records documenting the dates and amounts of the following:

- Study drug received
- Study drug dispensed to the subjects
- Study drug returned by the subjects
- Study drug returned to RADIUS/designee or destruction of study drug on site

Subjects will be instructed to return all used and unused study drug to the site. The study drug will be retained at the site until inventoried by the study monitor and approved for destruction or return. The study monitor will verify study drug records and inventory throughout the study.

7. STUDY PROCEDURES AND SCHEDULE

7.1. Study Procedures

The study-specific assessments are detailed in this section and outlined in [Table 1](#). Any results falling outside of the reference ranges may be repeated one time at the discretion of the Investigator.

7.2. Study Schedule

This study is comprised of six clinic visits. Study assessments are to be performed according to the Schedule of Events ([Table 1](#)). There is a \pm 4-day window for each clinic visit, other than the Day 1 for which there is a +4-day window and Month 4 visit for which there is a \pm 7-day window.

The study will consist of a Screening Period (up to 1 month), a Pretreatment Period (approximately 1 month), a Treatment Period (3 months), and a Month 4 Visit (one month). During the Treatment Period, subjects will have clinic visits for study-related protocol procedures at Day 1, Month 1, and Month 3. For the purpose of this study, one month is equal to 30 days.

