4. STUDY DESIGN

4.1. Description of the Study Design

This is an open-label, single-arm, multicenter study enrolling approximately 25 postmenopausal women with osteoporosis at approximately 5 study centers. The study is designed to measure the early effects of abaloparatide on tissue-based bone formation and resorption variables based on samples obtained by iliac crest bone biopsy after fluorochrome labeling. The study will consist of a Screening Period (up to 1 month), a Pretreatment Period (approximately 1 month), a Treatment Period (3 months), and a Month 4 visit one month after the last dose of study medication. Biopsies are to be obtained at 3 months of treatment for the following reasons:

- This is the optimal time for changes in biochemical markers of bone turnover to predict changes in BMD after 18 months of treatment with abaloparatide (Radius, Data on file)
- Longer periods of time increase the risk that the initial set of labels will be resorbed, which would seriously confound the results
- Comparisons to the 3-month results for teriparatide from the AVA Osteoporosis Study will be possible (Dempster, 2016)

Figure 1: BA058-05-020 Study Design, Including Schematic of Bone Biopsy Labeling Procedure

Full details of the protocol required assessments can be found in the Schedule of Assessments and Procedures ([Section 7.2.1](#)).

There will be a sub-study at selected sites to collect pQCT data and extend an additional 3 months of study drug administration for a total of 6 months of treatment.

Details of the schedule of measurements, endpoints and statistical analysis methods for the sub-study will be described in a separate document.

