7.2.1. Schedule of Assessments and Procedures

A comprehensive Schedule of Assessments and Procedures is presented in [Table 1](#).

Table 1: Schedule of Assessments and Procedures

Procedure	Visit 1	Visit 2 (±4 days)	Visit 3 (+4 days)	Visit 4 (±4 days)	Visit 5 (±4 days)	Visit 6 (±7 days)
	Screening (30 Days)	Pre-treatment	Day 1	Month 1	Month 3	Month 4
Informed consent	X					
Verification of entry criteria	X	X				
Review of medical history ^a	X	X	X	X	X	X
Physical examination ^b	X					
Symptom directed physical examination		X	X	X	X	X
Vital signs ^c	X	X	X	X	X	X
Weight and height measurements ^d	X		X	X	X	X
12-lead Electrocardiogram ^e	X		X		X	X
Urinalysis (dipstick) ^f	X		X	X	X	
Chemistry blood collection ^g	X		X	X	X	
Hematology blood collection	X		X	X	X	
Coagulation (PT and PTT) blood collection	X				X	
PTH (1-84)	X				X	
25-hydroxyvitamin D level	X					
1,25-dihydroxy vitamin D level	X					
FSH	X					
Thyroid stimulating hormone	X					
Injection training for subjects		X				
Dispense calcium and vitamin D supplements ⁿ	X	X	X	X		

Procedure	Visit 1	Visit 2 (±4 days)	Visit 3 (+4 days)	Visit 4 (±4 days)	Visit 5 (±4 days)	Visit 6 (±7 days)
	Screening (30 Days)	Pre-treatment	Day 1	Month 1	Month 3	Month 4
Study medication (abaloparatide) administration			Daily abaloparatide administration until and including the day of bone biopsy			
Demeclocycline (dispense and administration)		X ^h				
Tetracycline (dispense and administration)				X ⁱ		
Transiliac crest bone biopsy ^j					X	
Serum markers of bone metabolism (PINP and CTX)			X	X	X	
AP and lateral lumbar and thoracic spine radiographs	X					
Clinical assessment of new fractures ^k		X	X	X	X	X
Collect blood for immunogenicity testing			X		X	
BMD of lumbar spine, total hip, and femoral neck	X				X	
Investigator assessment of local tolerance (dermal reactions assessment)			X	X	X	
Subject diary review ^l			X	X	X	
Document AEs and concomitant medications ^m	At any time, question subject at each visit					
Drug supply/resupply/accountability		X	X	X	X	

^a Including alcohol and tobacco use assessment.

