7.2.10. Month 3/Early Termination (Visit 5)

- Review of medical history
- Symptom directed physical exam (see [Section 7.3](#))
- Blood pressure and vital signs (see [Section 7.3](#))
- Weight and height measurements (see [Section 7.3](#))
- 12-lead ECG

- Laboratory testing of serum chemistry (predose), hematology, and urine dipstick
- Coagulation blood testing
- PTH level
- Bone turnover markers (s-PINP and s-CTX)
- Clinical assessment of new fractures
- Collect blood for immunogenicity testing
- Review subject diary
- AE and concomitant medication review
- Self-administration of last dose of study medication when directed by site staff after completion of predose activities
- Investigator assessment of local tolerance after injection
- BMD assessments of lumbar spine, total hip and femoral neck by dual X-ray absorptiometry (DXA)
- Transiliac crest bone biopsy 5-8 days after last tetracycline dose (Sponsor together with the Medical Monitor should determine if included in Early Termination Visit)
- Drug accountability

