8. ADVERSE EVENT AND SERIOUS ADVERSE EVENT DOCUMENTATION

8.1. Evaluation of Safety

Timely, accurate, and complete reporting and analysis of safety information from clinical studies are crucial for the protection of subjects and is mandated by Regulatory Agencies worldwide. All clinical studies sponsored by RADIUS will be conducted in accordance with Standard Operating Procedures (SOPs) that have been established to conform to regulatory requirements worldwide to ensure appropriate reporting of safety information.

All AEs are collected from the time of the informed consent until 30 days after last dose of investigational product. Where possible, a diagnosis rather than a list of symptoms should be recorded. All AEs should be captured on the appropriate AE pages in the eCRF and in source documents. The Investigator will assess all AEs and determine reporting requirements to the Sponsor as well as the IRB.

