### **4.7.1 Adverse Events**

Analyses of AEs will be performed for those events that are considered to be treatment-emergent adverse events (TEAEs). A TEAE is defined as any AE that was absent (i.e., had not occurred) prior to the start of study drug and which occurs on or after the date of the first dose of study drug and within 30 days of the last dose of study drug, or any AE that started during the study period(s) prior to the start of study drug and worsened in severity after the start of study drug within 30 days of the last dose of study drug.

In any tabulation of adverse events, a subject contributes only once to the count for a given SOC or PT. For summaries by severity, a subject with multiple occurrences of an AE will be represented under the most severe occurrence. For summaries by relationship to study drug, a subject with multiple occurrences of an AE will be represented under the most related occurrence.

The number (%) of subjects with TEAEs will be summarized by SOC and PT. This analysis will also be performed for the following types of AEs: most common ( $\geq 5\%$ ) TEAEs, severe TEAEs, serious TEAEs (SAEs), TEAEs leading to study drug withdrawal, drug-related TEAEs (with probable or possible relationship to study drug), and AEs that are not treatment-emergent.

The number (%) of subjects with TEAEs will also be summarized by PT in order of decreasing frequency.

The number (%) of subjects with TEAEs by SOC and PT will also be tabulated by maximum severity (mild, moderate, or severe). A similar tabulation will be presented by relationship (related or not related) to study drug.

Subject listings will be provided for all AEs by SOC and PT. Listings will also be produced for AEs with outcome of deaths, severe AEs, SAEs, and AEs leading to study drug withdrawal.

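### In the main study, the last scheduled adverse-event enquiry may fall up to 7 days before the 30-day post-dose collection and TEAE period ends

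*Protocol*

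**What the plan says.** Protocol Section 4.1 describes "a Month 4 visit one month after the last dose of study medication". Section 7.2 fixes the unit: "For the purpose of this study, one month is equal to 30 days". The same section gives the final visit its slack, a "Month 4 visit for which there is a \pm 7-day window", and Table 1 repeats it. In the main study the last dose is taken in clinic at Visit 5; Section 7.2.10 lists "Self-administration of last dose of study medication when directed by site staff after completion of predose activities".

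On AEs, Protocol Section 8.1 states: "All AEs are collected from the time of the informed consent until 30 days after last dose of investigational product". Table 1 gives the method of elicitation as "At any time, question subject at each visit". Section 7.2.11 (Month 4) includes an AE and concomitant-medication review, and no later visit, call or diary review is scheduled for main-study subjects.

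SAP Section 4.7.1 counts as treatment-emergent a new event occurring "on or after the date of the first dose of study drug and within 30 days of the last dose of study drug". The collection period and the analysis period therefore agree at 30 days. The visit window is what does not match them.

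**The concern.** The plan promises AE data to post-dose day 30 and analyses them to day 30, yet the final visit at which the site must ask may be held a week earlier without any deviation. A subject seen on day 23 and one seen on day 37 are both compliant, but only the second has been asked about the whole period.

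The tables would not show the difference. SAP Section 3.11 analyses by nominal visit and Section 3.10 imputes nothing. The concomitant-medication tabulation in SAP Section 4.4 also runs to 30 days after the last dose and relies on the same final contact.

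Safety and tolerability is a listed endpoint (Protocol Section 3.2). The biopsy is taken at Visit 5, so this month also covers recovery from the procedure. At stake are the completeness and uniformity of TEAE ascertainment late in follow-up.

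**Working it through.** **Inputs**
- One month = 30 days (Protocol Section 7.2).
- Month 4 visit = one month after the last dose (Section 4.1), window ±7 days (Section 7.2, Table 1).
- Last dose at Visit 5, Month 3 (Section 7.2.10).
- AE collection to 30 days after the last dose (Section 8.1); TEAE window from first dose to 30 days after the last dose (SAP Section 4.7.1).

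**The plan's own interval.** Month 4 minus Month 3 = 4 × 30 − 3 × 30 = 30 days. This agrees with the stated one month.

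**Permitted range of the final visit**
- Earliest: 30 − 7 = post-dose day 23.
- Latest: 30 + 7 = post-dose day 37.

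**Shortfall** = max(0, 30 − day of final visit)
- Seen on day 23: 30 − 23 = 7 days (days 24 to 30).
- Seen on day 30 or later: 0 days.

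**Relative size at the early edge**
- Of post-dose follow-up: 7/30 = 23%.
- Of the TEAE window, taken as 90 days of treatment plus 30 of follow-up: 7/120 = 5.8%.

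**Average size, under an assumption.** The documents say nothing about when subjects attend. If visits fell evenly over the 15 days from 23 to 37, the mean shortfall would be (7 + 6 + 5 + 4 + 3 + 2 + 1)/15 = 28/15 = 1.9 days, or 1.9/120 = 1.6% of the TEAE window. The possible range is 0 days (nobody early) to 7 days (everybody at the early edge).

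**Subjects who stop dosing early.** Protocol Section 7.8 brings them back 30 days after the Early Termination visit. If the last dose was k days before that visit and the same ±7 days apply, the earliest final contact is day 23 + k and the shortfall is max(0, 7 − k). It disappears once k reaches 7.

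**Addendum subjects who complete six months.** Their final visit is Month 7, also ±7 days (Addendum Section 2), with the same 30-day AE period. The earliest final contact is again day 23. SAP Section 3.2 includes sub-study data in summaries only up to Month 4, so this gap affects listings and not summary tables.

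**With a 0/+7 window.** The final visit falls on days 30 to 37 and the shortfall is 30 − 30 = 0.

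**The case against.** The best case against the point is that ascertainment does not depend on visits alone. The duty to record AEs runs to day 30 whatever the visit date, and Table 1 allows documentation at any time. Serious events up to day 30 must be reported within 24 hours of awareness (Protocol Section 8.1.4), and related serious events remain reportable after completion. Open events are followed to resolution or stabilization (Section 8.1.5), so those subjects stay in contact, and unscheduled visits are provided for (Section 7.2.12). Nothing forbids a call on day 30. All of this stands. A reader might infer that days 24 to 30 are unobserved; the documents do not support that. What is missing is a scheduled prompt, which matters mostly for new, non-serious events.

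A reader might also infer that TEAE data will be incomplete. That requires a subject to attend early, have a new event afterwards and not report it, and the documents do not show how often this would happen.

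Nor should the gap be enlarged by counting both visits from Day 1. On that reading Visit 5 could be on day 90 + 4 = 94 and Visit 6 on day 120 − 7 = 113, only 19 days apart, for a shortfall of 11 days. The protocol anchors Month 4 to the last dose, so 7 days is the supported figure.

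Finally, safety is summarised descriptively in one arm without formal testing (SAP Section 4.7), so no treatment comparison can be distorted. That limits the importance of the mismatch but does not remove it.

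**Conclusion.** The mismatch is real and minor. A fully compliant main-study subject can have her last scheduled AE enquiry up to a week before the period reported by the SAP closes, and no other scheduled contact covers the difference. The 7 days are a worst case for a subject at the early edge and should be read against the whole TEAE window as well as the final month.

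The likely effect is some under-ascertainment of late, off-drug, mainly non-serious events, uneven between subjects according to attendance date. Its actual size cannot be derived from the documents. The primary endpoint, its test and the power are not involved.

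The conclusion rests on two readings: that the ±7 days apply around 30 days after the last dose, and that the last dose is taken at Visit 5 as scheduled.

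**What to change.** Make the Month 4 window one-sided, 0/+7 days from 30 days after the last dose, in Protocol Section 7.2 and Table 1, and carry it into the schedule reproduced in the SAP. The last scheduled AE enquiry then cannot precede day 30. An equivalent alternative is to keep the present window and add a telephone AE check on day 30 for anyone seen earlier.

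Make the same edit to Month 7 in the addendum so that the documents stay consistent, recognising that it improves the listings only.

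The cost is one window changed in a few places and slightly less freedom in booking the final visit or, under the alternative, one short call for each subject seen early.

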7.2.1. Schedule of Assessments and Procedures

A comprehensive Schedule of Assessments and Procedures is presented in [Table 1](#).

Table 1: Schedule of Assessments and Procedures

Procedure	Visit 1	Visit 2 (±4 days)	Visit 3 (+4 days)	Visit 4 (±4 days)	Visit 5 (±4 days)	Visit 6 (±7 days)
	Screening (30 Days)	Pre-treatment	Day 1	Month 1	Month 3	Month 4
Informed consent	X					
Verification of entry criteria	X	X				
Review of medical history ^a	X	X	X	X	X	X
Physical examination ^b	X					
Symptom directed physical examination		X	X	X	X	X
Vital signs ^c	X	X	X	X	X	X
Weight and height measurements ^d	X		X	X	X	X
12-lead Electrocardiogram ^e	X		X		X	X
Urinalysis (dipstick) ^f	X		X	X	X	
Chemistry blood collection ^g	X		X	X	X	
Hematology blood collection	X		X	X	X	
Coagulation (PT and PTT) blood collection	X				X	
PTH (1-84)	X				X	
25-hydroxyvitamin D level	X					
1,25-dihydroxy vitamin D level	X					
FSH	X					
Thyroid stimulating hormone	X					
Injection training for subjects		X				
Dispense calcium and vitamin D supplements ⁿ	X	X	X	X		

Procedure	Visit 1	Visit 2 (±4 days)	Visit 3 (+4 days)	Visit 4 (±4 days)	Visit 5 (±4 days)	Visit 6 (±7 days)
	Screening (30 Days)	Pre-treatment	Day 1	Month 1	Month 3	Month 4
Study medication (abaloparatide) administration			Daily abaloparatide administration until and including the day of bone biopsy			
Demeclocycline (dispense and administration)		X ^h				
Tetracycline (dispense and administration)				X ⁱ		
Transiliac crest bone biopsy ^j					X	
Serum markers of bone metabolism (PINP and CTX)			X	X	X	
AP and lateral lumbar and thoracic spine radiographs	X					
Clinical assessment of new fractures ^k		X	X	X	X	X
Collect blood for immunogenicity testing			X		X	
BMD of lumbar spine, total hip, and femoral neck	X				X	
Investigator assessment of local tolerance (dermal reactions assessment)			X	X	X	
Subject diary review ^l			X	X	X	
Document AEs and concomitant medications ^m	At any time, question subject at each visit					
Drug supply/resupply/accountability		X	X	X	X	

^a Including alcohol and tobacco use assessment.

^b A complete physical examination includes a review of the following systems: head/neck/thyroid, eyes/ears/nose/throat, respiratory, cardiovascular, lymph nodes, abdomen, skin, musculoskeletal, and neurological. Breast, anorectal, and genital examinations will be performed when medically indicated. After screening, any clinically significant abnormal findings in physical examinations not present at screening should be reported as AEs.

- ^c Vital signs include blood pressure (systolic and diastolic), temperature (oral), pulse rate, and respiratory rate. These will be assessed following a 5-minute rest (seated or supine) and before blood sample collection. At visits when study drug is administered at the site, vital sign assessments will be collected before the dose of study drug. Only blood pressure, pulse rate, and respiration rate are to be recorded one hour post-dose. Supine and standing blood pressure measurements will be performed at each visit during the Treatment Period.
- ^d Height is to be measured in the standing position with shoes off using a medical stadiometer.
- ^e An ECG will be recorded immediately prior to dosing and one hour post-dose during the Treatment Period.
- ^f All routine urinalysis will be performed on a sample freshly voided during the visit and sent to a central lab for microscopy if test is positive for microorganisms via dipstick.
- ^g Serum chemistry will be measured predose at Visits 3, 4, and 5.
- ^h Eighteen days before Day 1 of the Treatment Period (Visit 3), subjects who remain eligible for study participation will begin the first bone biopsy labeling procedure with administration of 150 mg demeclocycline 4 times daily for 3 days followed by a 12-day intermission, and then demeclocycline for 3 additional days at the same dose.
- ⁱ Approximately 23 to 26 days before Month 3 (Visit 5), subjects will begin the second bone biopsy labeling procedure with administration of 250 mg tetracycline 4 times daily for 3 days followed by a 12-day intermission, and then tetracycline for 3 additional days at the same dose.
- ^j Transiliac crest bone biopsy 5-8 days after last tetracycline dose. Sponsor Medical Monitor will decide if included in Early Termination Visit.
- ^k If the subject reports that a fracture has occurred, remind the subject to bring X-rays and any medical reports of the fracture to the next clinic visit. Documentation must be obtained on all new fractures that occur during the study. This documentation should be maintained in the source documents.
- ^l Subject will be instructed on completion of diary in the Pretreatment Period to include administration of medications for bone biopsy labeling procedure. The subject medication diary will be reviewed by study personnel at each study visit during the Treatment Period to ensure subject compliance.
- ^m AEs and SAEs will be recorded on the case report forms starting from the time of subject entry into the Screening Period (Visit 1) of the study (signed informed consent) until 30 days after the last dose of study medication. All AEs will be followed until resolution or stabilization. Any SAEs that occur at any time after completion of the study, which are considered by the Investigator to be related to study treatment, must be reported to the Sponsor or its designee.
- ⁿ Vitamin D supplements are required to be administered daily from the Pretreatment Period until the end of the Treatment Period. Calcium will also be administered daily, with the exception of the days of administration of demeclocycline and tetracycline where calcium administration will be withheld.

